There are currently no devices on the market for treatment of DE, however the anatomy of the penis allows for potential intervention. The main nerves to the penis branch off the pudendal nerve and provided sensory innervation allowing for stimulation and therefore are a potential target for treatment of DE. We therefore hypothesize that transcutaneous electrical stimulation of the nerves of the penis, either before or during sexual activity, may improve IELT. While there have been no animal or human studies in the literature looking at DE specifically, transcutaneous stimulation of branches of the pudendal nerve to treat a variety of urologic conditions has been done in the past. Laessoe et al demonstrated that transcutaneous vibratory stimulation of the penis can induce ejaculation as well as reduce detrusor overactivity within the bladder while Sonksen et al showed that perineal transcutaneous electrical stimulation can treat stress urinary incontinence.^{4,5} Transcutaneous penile nerve stimulation through vibration was shown in 66 patients with spinal cord injury to be successful in inducing ejaculation.⁶ Finally, Fode et al found in post-prostatectomy patients that transcutaneous penile nerve stimulation with vibration may be helpful in improving erectile function.⁷ While none of these studies examined DE specifically, they do demonstrated that transcutaneous stimulation of the penile nerves, or more proximal branches, can lead to observable effects within the structures they innervate which can be applied in treatment of DE.

7) Preliminary unpublished data (1 page maximum)

We performed a pilot study using a transcutaneous electric nerve stimulator (TENS 7000) with TENS pads applied directly to the penis in men with delayed orgasm. The study enrolled 14 men who wore the device during intercourse, before intercourse, and daily in serial fashion for 6 weeks each. Men completed validated questionnaires regarding sexual function as well as questions regarding device use/comfort. Approximately 40% of men reported subjective improvement with mean scores on intercourse and overall satisfaction showing increases. However, 64% of men reported problems with using the TENS pads on the penis which limited use.

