Using the feedback, we designed a unique wearable to continue this project based. The device use similar technology to other devices available online for neurostimulation of the penis. The device is connected to the TENS unit leads and uses conductive rubber to apply current directly to the skin. Instead of TENS pads there are two sets of conductive rubber tubes which pass current to stimulate penile nerves. The devices uses an elastic system to fit securely on the penis and deliver TENS stimulation. Men are provided guidance to use a similar range of stimulation parameters (e.g. Amplitude, voltage, frequency, pattern) to the TENS pad pilot study. The size of the device will prevent most men from using the device during intercourse. Rather the device will be used either before sex or daily (2 arms to the next proposed pilot study).

8) Experimental design and data analysis, including inclusion and exclusion criteria, statistical basis for the number of subjects to be enrolled, the statistical plan for analyzing at least the primary hypothesis, matrix showing procedure plan for each study visit, data safety monitoring plan (4 pages maximum)

We will be conducting a small clinical trial to test the safety and feasibility of a currently commercially available transcutaneous electrical nerve stimulator (TENS 7000) for treatment of delayed ejaculation.

This will involve enrollment of up to 12 men with a diagnosis delayed ejaculation. This number was chosen as the purpose of the study is to test the safety and feasibility of transcutaneous electrical stimulation of the penile nerves. Once an initial trial has been conducted, it would be expanded to more individuals for more robust statistical analysis. Our inclusion criteria are: men >18 years old and sexually active. Our exclusion criteria are: men <18 years old, not sexually active.

Due to the trial size (up to 12 men) to test safety and feasibility, we will not be able to perform a full statistical analysis but will rather be able to have men fill out a validated questionnaire on sexual function which encompasses questions that assess ejaculation.

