Subjects will be contacted via chart review at Stanford Healthcare as the single site involved in the study (phone script has been included in the IRB protocol). Many have already expressed willingness to participate including men who were enrolled in the original pilot study. Willing individuals will present to the urology clinic at Stanford at an assigned date and time. They will then be interviewed in a private clinic room with one of the trial staff. This interview will consist of outlining the study purpose and protocol, reviewing the consent form, and teaching on use of the device. After this is done, if they are interested in proceeding, they can sign the consent form and take it home to consider it more. Contact numbers will be provided at that visit. We will also provide them with a link to the Qualtrics survey to take before proceeding. After this visit, no further in person visits will be required. If they have any questions, they will be able to call the number provided. If they experience any adverse events, they will be instructed to contact us immediately.

Use of the device will be explained at their one and only in person clinic visit. They will be provided with a transcutaneous electrical nerve stimulator (TENS 7000) and shown how to use it as well as the range of settings for its use in DE. They will be shown how to apply the device to the penis. Participants will be able to use the device prior to sexual activity (immediately before sexual encounter for 10 minutes or daily for up to 14 days prior) to “prime” their system or during sexual activity. Each participant will use the device these three separate ways for 6 weeks each (total of 12 weeks of use).

Participants will have 12 weeks to use the device with follow up at each 6 week point filling out the same questionnaire via Qualtrics they filling out prior to beginning the study to quantify sexual and ejaculatory function.

The primary outcome is subjective improvement in the participants perception of their DE. Secondary outcomes will be assessed via the validated questionnaire International Index of Erectile Function (IIEF) which contains questions pertaining to ejaculation and sexual satisfaction.

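### No order of device modes is allocated and two 6-week modes fill the 12 weeks, so readings by mode are confounded with period, or with choice of order, and with possible carry-over

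*Protocol*

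**What the plan says.** Section 8 of the protocol puts every man through every mode: "Each participant will use the device these three separate ways for 6 weeks each". The same sentence gives the total as 12 weeks. Assessment follows the same rhythm: "Participants will have 12 weeks to use the device with follow up at each 6 week point filling out the same questionnaire via Qualtrics". The modes are described as use "immediately before sexual encounter for 10 minutes or daily for up to 14 days prior) to “prime” their system or during sexual activity".

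Section 7 counts the modes differently: "Rather the device will be used either before sex or daily (2 arms to the next proposed pilot study". It also describes the earlier pilot, whose 14 men "wore the device during intercourse, before intercourse, and daily in serial fashion for 6 weeks each".

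The size is given in Section 8: "This will involve enrollment of up to 12 men with a diagnosis delayed ejaculation". Nowhere does the protocol mention randomisation, an assigned or balanced order, a gap between modes, or a new baseline before the next mode. The order itself is not stated. The primary outcome, perceived improvement, is not tied to a mode or a time point.

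**The concern.** Each man gives one reading at the end of each 6-week period, and each period belongs to one mode. A reader will take the week-6 reading as the result for one mode and the week-12 reading as the result for the other. That works only if something separates mode from period, and the protocol provides nothing that does.

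Two influences can load onto the later mode:

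- **Period.** Growing practice with a new wearable, and drift over time in a self-rated outcome.
- **Carry-over.** Section 8 gives stimulation before sex a priming purpose, so the protocol itself expects some effect to outlast a session. The next mode follows at once.

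Section 7 treats the modes as distinct arms, and Section 8 looks ahead to a larger trial. If the readings by mode are used in planning that trial, a better later score could reflect time or carry-over rather than the mode. Order is set when each man starts, so under one common order no analysis plan could repair this afterwards.

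**Working it through.** **1. Duration.** The plan's own figure is 12 weeks in total, at 6 weeks per mode.

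- Three modes: 3 × 6 = 18 weeks, which overruns the stated total by 6. The 12 weeks are not reproduced.
- Two modes: 2 × 6 = 12 weeks, which matches and leaves 12 − 12 = 0 weeks for a gap.

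The mismatch is a separate defect. For the present point, neither reading leaves room for a gap.

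**2. Can mode be separated from period?** Take two modes, A and B, 12 men, and a model with an intercept, a period column (0, 1) and a mode column (A = 0, B = 1).

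- All 12 men in order AB: the period and mode columns are identical, so the matrix has rank 2 of 3. Mode and period are fully aliased.
- 6 men AB and 6 men BA: rank 3 of 3. Mode can be separated from period.

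With three modes in one common order the mode columns again equal the period columns, so the result is the same.

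**3. What carry-over could do (illustration).** Let p be the first-period response and f the share of first-period responders still improved at the end of period 2. I assume p = 0.40. The figure is borrowed from Section 7, where it describes the earlier TENS-pad pilot as a whole, not a first period with the new device. The documents give no value for f, so it runs from 0 to 1.

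- Second mode with no effect: apparent response = f × p.
- Second mode equally effective, responding independently: apparent response = 1 − (1 − p)(1 − f × p).

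| f | Period 1 | Period 2, inert mode | Period 2, equal mode |
|---|---|---|---|
| 0 | 40% | 0% | 40% |
| 0.25 | 40% | 10% | 46% |
| 0.50 | 40% | 20% | 52% |
| 1.00 | 40% | 40% | 64% |

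In men, 12 × 0.40 = 4.8 respond in period 1. At f = 0.50, 2.4 of 12 would count as improved on an inert second mode.

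**4. What a balanced order changes.** With 6 AB and 6 BA:

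- Equal modes: both average the same rate. At f = 0.50 this is (40% + 52%) / 2 = 46%. The false difference disappears, although both rates remain raised.
- A effective, B inert: A averages (40% + 40%) / 2 = 40%. B averages (0% + f × 40%) / 2, which is 10% at f = 0.50. This carry-over is unequal and is halved rather than removed. The first-period readings alone, 40% against 0%, are free of it.

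**5. Numbers per order.** Two modes: 12 / 2 = 6 men per order and 6 per mode in period 1. Three modes: 12 / 6 = 2 men per order and 12 / 3 = 4 per mode in period 1. As an example of precision, 2 of 6 improved has an exact 95% interval of about 4% to 78%.

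**The case against.** The strongest reply is that this is a feasibility pilot that does not compare modes. Much of that stands. The hypothesis in Section 5 concerns stimulation by either route, not a contrast between modes. The primary outcome is tied to no mode, Section 8 disclaims a full statistical analysis, and choosing a mode for the larger trial is never mentioned. The overall aim and a pooled reading of improvement are therefore not damaged by the order of modes.

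Three stronger readings are tempting, and the documents do not support them:

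- **That one fixed order is laid down.** It is not. The pilot's serial use suggests a common order, but Section 7 lists during, before, daily, while Section 8 lists before, daily, during. Full aliasing is conditional on one order being followed. If men or staff choose, the aliasing weakens but the choice becomes the confounder.
- **That an effect lasting 14 days is stated.** The wording "immediately before sexual encounter for 10 minutes or daily for up to 14 days prior" gives the length of stimulation before sex, not how long its effect lasts. The second questionnaire comes 6 weeks after the first mode ends. Carry-over at that point is possible, not shown.
- **That the problem survives any reconciliation.** The reference in Section 7 to two arms could be resolved as parallel groups, which would remove it. Section 8, however, says each man uses every mode.

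It is also fair to say that 12 men cannot settle which mode is better whatever the order. That limits what the fix can deliver. It does not excuse leaving order to chance or choice, since assigning it needs no extra men.

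**Conclusion.** The point holds as a design weakness of limited reach. As written, the week-6 and week-12 readings by mode cannot be attributed to the mode. Under one common order mode and period are inseparable, and under a chosen order the choice confounds them. The finding on period rests on the design alone and needs no assumed figure.

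The carry-over part is weaker. The priming rationale makes it plausible, but its size is unknown. On an assumed 40% first-period response, a second mode with no effect could show anything from 0 to 40% improved. That range describes uncertainty and is not an estimate of bias.

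A reader might infer that the trial's main conclusion is compromised. The documents do not support that: no test between modes is planned, and the safety and feasibility aim stands. What is affected is any reading by mode and any use of it to plan the expanded trial.

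**What to change.** First reconcile Sections 7 and 8 on the number of modes and on 12 against 18 weeks. Which version is right is for the investigators to decide.

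If each man still uses every mode, amend Section 8 as follows:

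- Assign each man at the single clinic visit to an order of modes from a pre-made balanced list: for example, 6 men per order for two modes, or 2 men in each of the 6 orders for three.
- Present first-period results by mode as the estimate free of carry-over from another period of this study. Section 8 allows men from the earlier pilot to join, so previous exposure should be noted.
- Label later-period results as cumulative.
- State that any difference between modes is descriptive only.

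The cost is one amendment and one list, with no added men, visits or questionnaires. There are two downsides. First-period results rest on about 6 (or 4) men per mode, fewer if enrolment stops short of 12, and are very imprecise. Balanced order removes the period bias from mode readings but not unequal carry-over.

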Transcutaneous Electrical Nerve Stimulation of Penile Nerves for Treatment of Delayed Ejaculation

Study Protocol

NCT04115540

April 19, 2021

Scientific Protocol

1) Name of study

Transcutaneous electrical stimulation of the penile nerves for delayed ejaculation

2) PI and other key investigators or key study personnel

[name] (PI) and [name]

3) Specific source of institutional funding (account number)

No institutional funding

4) List of sources from whom you are seeking funds (or have sought funding) for this project

Urology Department, Stanford University School of Medicine

5) Specific aims and basic hypothesis including an explicit primary hypothesis or goal

The aim of this clinical trial is to test the safety and feasibility of using transcutaneous electrical nerve stimulation of the penile nerves to reduce ejaculatory latency in men with delayed ejaculation. We hypothesize that this type of stimulation, either before or during sexual activity, will reduce ejaculatory latency time.

6) General background (2 page maximum including published preclinical and animal data supporting basic hypothesis, if relevant)

Delayed ejaculation (DE) is a condition in which men suffer a delay of intravaginal ejaculatory latency time (IELT) of more than 21-23 minutes.¹ Due to variations in definition and inherent difficulty in characterizing the prevalence of the condition, the epidemiology is varied.

However, the prevalence ranges in the literature from about 1-4% with the true incidence believed to be higher.^{1,2} Current treatment for DE is either counseling or off label pharmaceuticals. Counseling generally involves addressing a known underlying psychogenic cause and can involve such interventions as cognitive behavioral therapy, sex therapy, or psychotherapy.³ However, these techniques can offer be time consuming and their efficacy varies greatly. Off label medications are the only current pharmacotherapy available for the treatment of DE. Various medications have been used off-label such as ephedrine, bupropion, and oxytocin. While some of these medications improve IELT, they remain cumbersome as they are daily medications and have potential serious adverse side effects.^{2,3}

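### Section 8 gives each man three modes of use at 6 weeks apiece but totals them as 12 weeks, not 18, and the third mode conflicts with Section 7

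*Protocol*

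**What the plan says.** Section 8 lists three ways to use the device: for 10 minutes immediately before a sexual encounter, daily over a period of up to 14 days beforehand, and during sexual activity. It then says "Each participant will use the device these three separate ways for 6 weeks each (total of 12 weeks of use". The following paragraph repeats the total and sets the assessments: "Participants will have 12 weeks to use the device with follow up at each 6 week point". Device use is taught at a single clinic visit, and "After this visit, no further in person visits will be required".

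Section 7 describes the redesigned device: "The size of the device will prevent most men from using the device during intercourse". Its next sentence reads "Rather the device will be used either before sex or daily (2 arms to the next proposed pilot study". The same section describes the earlier TENS-pad pilot: "The study enrolled 14 men who wore the device during intercourse, before intercourse, and daily in serial fashion for 6 weeks each".

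The hypothesis still covers both timings. Section 5 has "either before or during sexual activity, will reduce ejaculatory latency time" and Section 6 has "either before or during sexual activity, may improve IELT".

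**The concern.** The sentence in Section 8 fixes what each man does and for how long, and its own numbers disagree. It also gives every man a mode that Section 7 has set aside for this device.

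The consequence is practical. With one teaching visit, there is no later scheduled visit at which wrong instructions could be put right. After baseline, the only scheduled outcome assessments are the online questionnaires at weeks 6 and 12. In a feasibility study of up to 12 men, the modes used, their length and the timing of assessment are the core of the design. Participants also have to be told whether they are committing to 12 or 18 weeks.

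**Working it through.** **Inputs**

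- Modes per participant: 3 (Section 8)
- Weeks per mode: 6 (Section 8)
- Stated total: 12 weeks (Section 8, given twice)
- Questionnaires after baseline: every 6 weeks within 12 weeks, so weeks 6 and 12 (Section 8)
- Modes planned for the new device: 2, before sex and daily (Section 7)
- Earlier pilot: 3 modes in series, 6 weeks each (Section 7)

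**Step 1: the plan's own total.** Total = modes × weeks per mode = 3 × 6 = 18 weeks. The stated 12 is not reproduced. The gap is 18 − 12 = 6 weeks, which is 6/12 = 50% of the stated total, or 6/18 = 33% of the three-mode total. It equals one whole mode.

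**Step 2: readings that might rescue the 12.**

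- Two modes: 2 × 6 = 12. This gives the total but contradicts the stated count of three.
- Three shorter modes: 12 / 3 = 4 weeks each. This contradicts the stated 6 weeks each.
- Both uses before sex counted as one mode, plus use during sex: 2 × 6 = 12. This again contradicts the count of three, and the pair differs from Section 7's pair.
- Overlapping modes: this contradicts the description of the modes as separate, and a questionnaire could not be attributed to one mode.

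**Step 3: modes against questionnaires at weeks 6 and 12.**

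| Schedule | Mode ends (weeks) | Modes without an end-of-period questionnaire |
|---|---|---|
| 3 modes × 6 weeks | 6, 12, 18 | 1 of 3 |
| 3 modes × 4 weeks | 4, 8, 12 | 2 of 3 (week 6 falls midway through the second mode) |
| 2 modes × 6 weeks | 6, 12 | 0 of 2 |

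Two modes need baseline plus 2 questionnaires per man. Three 6-week modes need baseline plus 3.

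**Step 4: Section 7 against Section 8.** Section 7 names two modes for the new device, before sex and daily. Section 8 names those two plus use during sexual activity, and gives all three to every man. The pilot's schedule, 3 × 6 = 18 weeks, has the same three modes and the same 6-week periods as Section 8. The wording was plausibly carried over from there, though that is an inference. The 12-week total, the 6-week follow-up points and Section 7's two modes all agree on 2 × 6 = 12.

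**The case against.** The best case on the other side accepts the arithmetic and disputes reach and weight.

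- **The size statement is limited.** Section 7 says most men, not all, and speaks of intercourse, whereas Section 8 speaks of sexual activity, which is wider. This is fair. The conflict rests mainly on Section 7's next sentence, which confines planned use to two modes, and it survives on that sentence.
- **The hypothesis is not contradicted.** An either/or hypothesis is compatible with a trial that tests only use beforehand. This also stands: the edits to Sections 5 and 6 are for alignment and do not correct an error.
- **The missing questionnaire is not a second defect.** If three modes were meant and 12 is the slip, follow-up every 6 weeks would naturally extend to week 18. That is right; the gap arises only if the 12-week limit governs. The 4-week schedule is likewise hypothetical, since the text says 6 weeks each.
- **The reference to two arms is ambiguous.** It could mean parallel groups, two orders or loose wording. Section 8 has each man use every mode, and 6-week parallel arms would give each man only 6 weeks, so sequence is the better reading. The investigator must still confirm it.
- **Severity.** The study is small, plans no full statistical analysis, and its likely intent can be recovered. Even so, the sentence is an instruction for delivering the intervention, and it cannot be followed as it stands.

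**Conclusion.** The concern holds, and the text must be fixed. Section 8's schedule is 18 weeks against a stated 12, a discrepancy of 6 weeks or one full mode, and its third mode conflicts with Section 7. If the 12-week limit governs and the modes are used one after another, one of three modes has no end-of-period questionnaire.

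The arithmetic needs no assumption beyond the modes being separate, as the protocol says. That two modes were intended is an inference from three features of the protocol that agree, and it is for the investigator to confirm. Duration and mode of use belong in the protocol, so a separate analysis plan would not resolve the conflict.

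**What to change.** Unless the investigator intends three modes:

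- **Section 8:** limit use to two modes, 10 minutes immediately before a sexual encounter and daily for up to 14 days beforehand. State that each man uses both in sequence, 6 weeks each, 12 weeks in total, with the questionnaire at the end of each mode (weeks 6 and 12). Delete use during sexual activity.
- **Section 7:** replace the reference to two arms with two sequential modes, once the investigator confirms that this is the design.
- **Sections 5 and 6:** for consistency, limit the hypothesis to stimulation before sexual activity.

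This costs a short protocol amendment and matching participant instructions. It adds no patients, visits or questionnaires.

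If the third mode is kept, restate both the total and the period of use as 18 weeks, add a week-18 questionnaire, and explain how use during sexual activity is feasible given what Section 7 says about device size. That adds 6 weeks and one questionnaire per man.

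### Safety and feasibility are the stated aim and the reason for the sample size, yet no safety or device-use outcome is named and no scheduled adverse event enquiry is described

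*Protocol*

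**What the plan says.** Section 5 of the protocol opens with the aim: "The aim of this clinical trial is to test the safety and feasibility of using transcutaneous electrical nerve stimulation of the penile nerves", in order to shorten ejaculatory latency. Section 8 sets the sample size at up to 12 men and explains it the same way: "This number was chosen as the purpose of the study is to test the safety and feasibility". It adds that a full statistical analysis will not be possible and that the investigators "will rather be able to have men fill out a validated questionnaire on sexual function".

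The outcomes are named later in section 8. "The primary outcome is subjective improvement in the participants perception of their DE"; the secondary outcomes come from the IIEF.

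There is one clinic visit. After that, two channels are described:

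- **Adverse events:** "If they experience any adverse events, they will be instructed to contact us immediately".
- **Scheduled follow-up:** at each 6-week point, "filling out the same questionnaire via Qualtrics they filling out prior to beginning the study to quantify sexual and ejaculatory function".

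Section 7 describes the preceding pilot in 14 men. "Men completed validated questionnaires regarding sexual function as well as questions regarding device use/comfort". It reports that "64% of men reported problems with using the TENS pads on the penis which limited use", and says that the new wearable was designed from that feedback.

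**The concern.** What the trial is for and what it is set up to measure do not match. Both named outcomes concern benefit or sexual function. Nothing named as an outcome measures harm, comfort, ease of use or amount of use.

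The described data collection does not make up for this. A questionnaire first completed before the device is used, with the stated purpose of measuring sexual and ejaculatory function, is not described as asking about events or problems during use. Otherwise the team learns of harm only when a participant takes the initiative.

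Two things are at stake. First, a low adverse event count could mean few events or few reports, and the data would not tell them apart. Second, the device was changed because men had trouble using the pads, yet no described item would show whether the change helped. With no record of use, a lack of perceived improvement could not be separated from a lack of use. Section 8 foresees expansion to more men after this trial, so these are the answers the next step would need. An analysis plan cannot later supply answers that were not requested.

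**Working it through.** **Sample size.** The protocol gives no event rate, precision target, power or effect size behind 12, so there is no calculation to reproduce.

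**Aim set against measurement.**

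| Component of the aim | Outcome named in section 8 | Scheduled collection described |
|---|---|---|
| Safety | None | None; participant-initiated contact only |
| Feasibility, read as shortening latency | Perceived improvement bears on it | 6-weekly survey |
| Feasibility, read as device use and comfort | None | None described |

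The heading of section 8 also lists a data safety monitoring plan among its contents. The only safety procedure in the text beneath it is the instruction to make contact.

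**What 12 men can show if every event is captured.** Input: n = 12 (section 8), zero men with an event. The exact (Clopper-Pearson) two-sided 95% upper limit is

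1 − 0.025^(1/12) = 0.2646, or 26.5%.

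This comes from n = 12 and stays the same after the fix. It is a limit on the true event rate only if all events are recorded.

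**Illustration of incomplete reporting.** The reporting fractions r below are assumptions; the protocol gives none. With true rate p per man, the chance that the team learns of at least one affected man is 1 − (1 − p·r)^12.

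| True rate p | r = 100% | r = 50% | r = 25% |
|---|---|---|---|
| 5% | 46.0% | 26.2% | 14.0% |
| 10% | 71.8% | 46.0% | 26.2% |
| 20% | 93.1% | 71.8% | 46.0% |

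For example, at p = 10% and r = 50%: 1 − 0.95^12 = 0.460. The table shows the direction of the effect and a possible range. It does not estimate the effect in this trial.

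**How common the usability problem was in the pilot.** Inputs: 64% and 14 men (section 7). 0.64 × 14 = 8.96, so the count is 9, and 9/14 = 64.3%. The neighbouring counts do not fit: 8/14 = 57.1% and 10/14 = 71.4%. The exact 95% CI for 9/14 is 35.1% to 87.2%, assuming all 14 men answered. Even the lower limit is about a third of men.

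**Number of survey points.** Section 7 describes two patterns of use, and 2 × 6 = 12 weeks. Section 8 describes three patterns of 6 weeks each, and 3 × 6 = 18 weeks, but states 12 weeks in total. The survey count is therefore two or three, depending on how these passages are reconciled.

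**The case against.** The strongest reply is that much of this is read from silence in a short form. Section 8 is limited to four pages, and it refers to an IRB protocol and a consent form that are not at hand; safety procedures may be set out there. The survey items are not listed either. The wording that follow-up repeats the baseline questionnaire may be loose: if perceived improvement is asked directly as a change, that item could hardly appear at baseline, so the follow-up form may hold more than is described. The trial continues a pilot that did ask about use and comfort.

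This stands as far as it goes. The finding is that such items are not described, not that they are known to be absent. It does not answer the main point, because no safety or device-use outcome is named whatever the survey contains. Naming outcomes and stating how adverse events are collected are protocol matters that are not normally left to an analysis plan.

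A second reply is that feasibility in section 5 is tied to shortening latency, so perceived improvement already covers part of it. That is fair and is accepted for that part. Safety remains uncovered, and the pilot's 64% makes device use a reasonable thing to measure.

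A third reply is that the figures do not measure the defect. The 26.5% limit is a consequence of 12 men, and the 64% refers to pads rather than the new device. Both statements are correct. The figures give context, and the loss from relying on spontaneous reports cannot be sized from the protocol.

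**Conclusion.** The concern holds and should be fixed. Safety and feasibility are the declared aim and the only reason given for up to 12 men, but the protocol names no safety or device-use outcome and describes no scheduled enquiry about adverse events.

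Confidence is high that these are not described. Whether the survey in fact contains such items cannot be judged from this document. If it does not, the trial could finish without systematically collected data on safety or on the usability problem that prompted the redesign. Full capture is the condition for reading 0/12 as an upper limit of 26.5%, and spontaneous reporting alone does not ensure it. The pilot interval assumes a denominator of 14.

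**What to change.** **Data collection.** At each scheduled survey, add a short fixed block:

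- an adverse event checklist: yes or no, severity, and whether the event occurred with device use or was attributed to it;
- the pilot's use and comfort items, reworded where they refer to pads;
- the number of times the device was used.

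If the survey already contains such items, describe them in the protocol. Keep the existing instruction to report adverse events at once.

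**Outcomes.** Alongside the existing ones, name two descriptive outcomes, each with an exact 95% CI:

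- the proportion of men with any adverse event, and with any attributed to the device;
- the proportion with a problem that limited use.

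Treat any comparison with the pilot's 64% as descriptive only, since section 8 allows for pilot men to take part again.

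**Schedule.** Reconcile the use patterns in sections 7 and 8 so that the number of survey points is fixed.

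**Cost.** A few items at two survey points, or three if three 6-week periods are meant, and two outcome definitions. No visit is added and the sample size does not change. The survey becomes slightly longer, the recorded adverse event count will probably rise, and use counts recalled over 6 weeks will be approximate.
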